7.8 Examination of Facial Motor Nerves

Observe:

1. Face at rest for any facial asymmetry not apparent at baseline.
2. Any facial tics, asymmetry of eye blinking or eye closure
3. During smiling

In Palsy:

1. Blink: The eyelid on the affected side closes just a trace later than the opposite eyelid.
2. Nasolabial folds: The weaker one is flatter.
3. Mouth: The affected side droops and participates manifestly less in speaking.

Subjects experiencing motor nerve adverse events will be considered resolved when their motor nerve assessment returns to baseline observations by study investigator.

7.9 Burn Depth Assessment (Burn Adverse Events Only)

Burn depth assessment may be difficult, **Table 4** aids in accurate estimation of burn depth, should a burn adverse event be reported. Suspicion of deep partial thickness or full thickness burns warrants notification of study Sponsor.

Table 4. Burn Depth Assessment

Depth	Cause	Surface/color	Pain sensation
Superficial	Sun, flash, minor scald	Dry, minor blisters, erythema, brisk capillary return	Painful
Superficial Partial thickness - (superficial dermal)	Scald	Moist, reddened with broken blisters, brisk capillary return	Painful
Deep Partial thickness - (deep dermal)	Scald, minor flame contact	Moist white slough, red mottled, sluggish capillary return	Painless
Full thickness	Flame, severe scald or flame contact	Dry, charred whitish. Absent capillary return	Painless

8 ADVERSE EVENTS ASSESSMENT REPORTING

8.1 Adverse Events Evaluation

Safety evaluations for this study include an interview with the study subject at each follow-up visit by the Investigator or Research Coordinator to elicit information about any medical occurrence that meets the definition of Adverse Event. This information will be documented in CRF without regard for cause or relation to device and/or procedure.

In addition, study subjects will be instructed in the Informed Consent Form, post-procedure take-home instructions, and verbally by study staff to report all complications experienced post study procedure to the site personnel as soon as they occur/are observed. Study staff will ensure that monitoring and management of all adverse events is prioritized. To ensure this, study staff will contact (phone, text, email, video call at subject's preference) all subjects with ongoing Adverse Events at the following time points, as applicable:

- 21 (± 5) days
- 45 (± 5) days
- 60 (± 5) days
- 75 (± 5) days
- 105 (± 5) days
- 120 (± 5) days
- 135 (± 5) days
- 150 (± 5) days
- 165 (± 5) days

Three attempts will be made to contact the subject before considering the subject contact visit missed and protocol deviation recorded. If subjects are unable to be contacted via their preferred method of contact, another method of contact may be utilized.

Subjects may be asked to come into the site at any time to assess adverse events.

Study investigators are provided liberty to mitigate adverse events as deemed necessary per IHC GCP Guidelines E6(R2)4.3.2 which states "During and following a subject's participation in a trial, the investigator/institution should ensure that adequate medical care is provided to a subject for any adverse events related to the trial".

Adverse event resolution dates will be determined by investigator using either in-person or remote (phone, video call, text, email, etc.) examinations or communication with the subject. To ensure the most accurate reporting of adverse event durations, investigators are instructed not to wait until scheduled office follow-up visits to assess resolution.

It is the Investigator's responsibility to determine seriousness, severity, and relatedness of the Adverse Event to the device and procedure using the definitions below.

8.2 Adverse Event (AE) Definition

An **adverse event** (AE) is any untoward or unfavorable medical occurrence in a human subject, including any abnormal sign (for example, abnormal physical exam or laboratory finding), symptom, or disease temporally associated with the subject's participation in the research, whether or not considered related to the subject's participation in the research.

A preexisting condition (one that is present at the start of the study) will be recorded as an AE only if the frequency, intensity, or the character of the condition worsens during the study period. Neither the condition, hospitalization, prolonged hospitalization, nor surgery are reported as an AE in the following circumstances: hospitalization or prolonged hospitalization for diagnostic or elective surgical procedures for a preexisting condition. Surgery should not be reported as an outcome of an AE if the purpose of the surgery was elective or diagnostic and the outcome was uneventful.

8.3 Serious Adverse Event (SAE) Definition

Serious Adverse Event (SAE) is an adverse event that:

- Led to a death or
- Led to a serious deterioration in the health of a subject that:
 - Resulted in a life-threatening illness or injury,
 - Resulted in a permanent impairment of a body structure or body function,
 - Required in-patient hospitalization or prolongation of existing hospitalization,
 - Resulted in medical or surgical intervention to prevent impairment to body structure or a body function, or
 - Led to fetal distress, fetal death or a congenital abnormality or birth defect.

All SAEs that occur during the study period, whether considered to be related to the study device or not, must be reported to the Sponsor within 24 hours of knowledge of the event. IRB reporting requirements may also apply for SAEs.

8.4 Unanticipated Adverse Device Effect (UADEs) Definition

An **unanticipated adverse device effect (UADEs)** is defined as any serious adverse effect on health or safety or any life-threatening problem or death caused by, or associated with, a device, if that effect, problem, or death was not previously identified in nature, severity, or degree of incidence in the investigational plan, or any other unanticipated serious problem associated with a device that relates to the rights, safety, or welfare of subjects.

In addition, any **UADEs** will be reported to the Sponsor and the reviewing IRB as soon as possible, but no later than within 24 hours of knowledge of the event.

All adverse events, anticipated or unanticipated, will be monitored until they are adequately resolved or explained.

8.5 Reporting Requirements

All Adverse Events (AEs) and Expected Treatment Effects (ETEs) observed by study subjects, investigators, or other study staff from first exposure to the study product through last study follow-up visit will be recorded. If a device-related AE, ETE, SAE, or unanticipated serious

device related effect is ongoing at the final study visit, the subject will be followed until resolution, until the condition stabilizes, until the event is otherwise explained, or the subject is lost to follow-up. The investigator should make every effort to ensure that follow-up includes any supplemental investigations as may be indicated to elucidate, as completely as practical, the nature and/or causality of the AE or SAE. This may include unscheduled follow up visits for AE assessment.

Study subjects will be instructed in the ICF, post-treatment take home instructions, and verbally by study staff to report all AEs to the clinical study staff. AE information will be collected throughout the duration of the study and recorded on CRFs. Subjects experiencing ongoing adverse events will be contacted as per **Section 8.1**.

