5.2 Study Population

Sections 5.2.1 and 5.2.2 represent the eligibility criteria for this study. Subjects who plan to undergo a procedure for the purpose of improving the appearance of lax tissue in the neck and submental region from each participating investigator's subject population and meet the eligibility criteria as defined within this protocol will be enrolled in the study.

Subjects will be considered enrolled into the study when they have signed an approved informed consent form, meet all study criteria, and have undergone the study procedure.

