6.3 Study Procedure

On the day of the procedure and prior to the study procedure, female subjects with child-bearing potential must complete a urine pregnancy test (result must be obtained prior to the procedure).

Medications at investigator discretion may be provided as follows:

- Optional for Procedure (given within 90 minutes prior to procedure):
 - Ativan 2mg or Valium 10-20mg
 - Norco 5-10mg, Hydrocodone 5-10mg, or Ultram 200mg

A responsible driver (friend or family member) is required if these medications are prescribed.

During the study procedure, subjects will be treated with the Renuvion APR device according to the product IFUs and procedures described in this section of the protocol. The bilateral treatment area includes the tissue of the neck (to the posterior border of the sternocleidomastoid muscle) and submental area. Treatment will be performed through three (3) incisions (2 periauricular and 1 submental) with each incision large enough to allow for gas egress, see **Figure 1**. Each incision site will be anesthetized with 1% or 2% Lidocaine with Epinephrine (1:100,000) prior to incision being made.

[figure not shown]

Figure 1: Treatment incisions (2 periauricular and 1 submental).

The treatment area will be infused with standard of care tumescent solution referred to as a Klein solution. The solution consists of 1% or 2% Lidocaine (Plain) to make a 0.2% concentration (double Klein) and Epinephrine 1mg/1ml (1:1,000) and optional Sodium Bicarbonate 8.4% added to Normal Saline or Lactated Ringers. Infuse area with 150-250cc or until the area is taut. To prevent lidocaine toxicity, 35-55mg/kg should not be exceeded¹⁶.

Once infused with Klein solution, undermining of the tissue in the area to be treated will be performed using a cannula 3-4mm in diameter. No energy (i.e. radiofrequency, ultra-sound, or laser energy) or suction will be used during the undermining of the tissue.

After undermining, the Renuvion APR device treatment will be performed using 4-6 treatment passes with settings of 70% power and 1.5 LPM of helium flow with an activation speed of approximately 1-3 cm/s. Prior to performing treatment through each one of the three (3) incisions, the investigator will evaluate activation speed by performing the following steps in the sterile field at a safe distance from the subject:

1. Using a sterile ruler, two parallel lines will be drawn in the sterile field that are 10cm apart.

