9.2 Risks

This treatment modality was designed to inherently minimize the risk to the subject. However, treatment with energy-based modalities (laser, radiofrequency, and plasma devices) produce subsequent heating of the soft tissue that could involve the following commonly Expected Treatment Effects (ETEs): discomfort/pain, edema, erythema, ecchymosis, hypoesthesia, temporary sensory nerve injury (touch sensitivity, itching, temporary numbness/tingling), transient migratory firmness, and temporary and/or transient crepitus.

In addition to commonly expected treatment effects, treatment with the Renuvion APR device could involve the following risks: helium embolism into the surgical site due to inadvertent introduction into the venous or arterial blood supply system, unintended burns (deep or superficial), pneumothorax, temporary or permanent motor nerve injury, ischemia, fibrosis, infection, gas buildup, bleeding, hematoma, seroma, subcutaneous induration, pigmentation changes, increased healing time, unsatisfactory scarring, asymmetry and/or unacceptable cosmetic result.

Subjects using drugs that reduce coagulation (aspirin or NSAIDs) may experience increased bruising or bleeding at the treatment site.

A grounding pad is used to ground/neutralize the electrical current. Subjects undergoing radiofrequency treatment will be kept away from contact with metal parts which are grounded, or which have appreciable capacitance to earth.

Risks associated with tumescent anesthesia (lidocaine and epinephrine) include blurred vision, mental/mood changes, drowsiness, dizziness, unusually slow heartbeat, rash, itching, swelling, anxiety, apprehensiveness, restlessness, tremor, weakness, sweating, palpitations, pallor, nausea and vomiting, headache, and respiratory difficulties.

Side effects and subject instructions for medications that are at investigator discretion include:

- **Keflex**

If any of these effects persist or worsen, tell your doctor or pharmacist promptly:

- Diarrhea
- Nausea
- Vomiting
- Upset stomach

This medication may rarely cause a severe intestinal condition due to resistant bacteria. This condition may occur during treatment or weeks to months after treatment has stopped. Do not use anti-diarrhea or opioid medications if you have any of the following

symptoms because these products may make them worse. Tell your doctor right away if you develop:

- Persistent diarrhea
- Abdominal or stomach pain/cramping
- Blood/mucus in your stool

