8 ANALYSIS POPULATIONS AND HANDLING MISSING DATA

8.1 Analysis Sets and Handling of Missing Data

8.1.1 Full Analysis Dataset

(Intent-to-Treat Sample, ITT)

The ITT sample will be used in the primary safety analysis. This is defined as the subjects who enrolled in the trial and on whom the procedure was initiated at least to the point where energy from Renuvion entered the subject’s skin.

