9.4 Statistical Analysis of Additional Endpoints

These analyses will be performed by data type as described in **Section 9.1** of this SAP. All analyses will be descriptive (i.e., no hypotheses will be tested). All of the various AE rates will be estimated using methods for time-to-event data for each category of AE, with emphasis on all device- and procedure-related AEs, and serious device- and procedure-related AEs. Analyses are planned as per **Table 5**.

The assessment tools (e.g. the GAIS and Subject Satisfaction Survey) can be found in the study protocol.

Table 5: Analyses of Additional Endpoints

Endpoint Number	Endpoint	Type of Analysis	Comments
1	The improvement in the appearance of lax tissue in the neck and submental region at 90 days compared to baseline as determined by qualitative 2D photography assessment by blinded Independent Photographic Reviewers.	Categorical	This endpoint is identical to the primary effectiveness endpoint except that it is at 90 days; however, no hypothesis will be tested.
2	Subject Modified Global Aesthetic Improvement Scale (GAIS) at 180-day FUV	Categorical	
3	Investigator Modified GAIS at 180-day FUV	Categorical	
4	Subject satisfaction with procedure recorded at the 180-day FUV on the Subject Satisfaction Survey	Categorical and Continuous	Categorical on 1-4 and Continuous on 5

Endpoint Number	Endpoint	Type of Analysis	Comments
5	Quantitative improvement at 180-days as determined by quantitative assessment based on 2D photography: a) Proportion responders (those achieving at least 20 mm ² of lift of the submental region). b) Average mm ² of improvement.	Categorical and Continuous	Categorical on a and Continuous on b
6	Quantitative improvement at 180-days as determined by quantitative assessment based on 3D photography - Average cc of Total Volume change.	Categorical and Continuous	Categorical on a and Continuous on b
7	The evaluation of adverse events up to the 180-day visit following treatment.	Time-to-event	
8	The evaluation of pain scores through the 30-day follow-up visit as reported by the subject on a Numeric Rating Scale (NRS).	Categorical	

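### AE recording opens at first device exposure, after anesthesia and undermining, so short-lived non-serious events before energy need not be recorded and subjects stopped before energy belong to no analysis set

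*Protocol*

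**What the plan says.** **Recording window.** Protocol 8.5 covers AEs and expected treatment effects observed "from first exposure to the study product through last study follow-up visit will be recorded". The synopsis names the Renuvion APR handpiece as the study device, so the natural reading is that the window opens at first use of that device on the subject.

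**Order of the procedure.** Protocol 6.3 puts several steps before the device: optional sedative and opioid; local anesthetic ("Each incision site will be anesthetized with 1% or 2% Lidocaine with Epinephrine (1:100,000) prior to incision being made"); three incisions; tumescent infusion; and cannula undermining. Device passes come last.

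**Recognised hazards of those steps.** Protocol 9.2 has a paragraph beginning "Risks associated with tumescent anesthesia (lidocaine and epinephrine) include", whose list runs to palpitations and respiratory difficulties. Protocol 8.7 names edema, hematoma, nerve injury and pain as events of tumescent anesthesia or undermining, to be classed as procedure related.

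**Who counts.** Protocol 5.2 treats subjects as enrolled when they have signed consent, "meet all study criteria, and have undergone the study procedure". SAP 8.1.1 limits the ITT set to enrolled subjects "on whom the procedure was initiated at least to the point where energy from Renuvion entered" the skin, and states: "The ITT sample will be used in the primary safety analysis".

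**What is reported.** SAP 9.4 estimates AE rates by category, "with emphasis on all device- and procedure-related AEs".

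**The concern.** Procedure-related AEs are a class of their own in this plan, and much of what can cause them happens before any energy is delivered. A recording rule tied to the device starts the clock after those causes have begun to act. A population rule tied to the device removes anyone who did not get that far.

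The second part matters more. A procedure abandoned during infusion or undermining may well have been abandoned because the subject reacted badly. Such subjects are selected by harm, so leaving them out is not neutral. The rates at stake are the procedure-related AE rates. The effectiveness and pain tests are not involved.

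**Working it through.** **1. The plan's own figure.** The documents give no rate of pre-energy events or aborted procedures, so there is no figure on this point to reproduce. The only nearby figure is the power in Protocol Table 5, which 11.1.2 also applies to the safety test. With N = 60 and rejection at 41 or more, the exact binomial gives P(X ≥ 41 | 0.55) = 0.0246 and P(X ≥ 41 | 0.75) = 0.9075, matching the stated 0.90752. Nothing below changes it.

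**2. Recording rules by timing of the event.**

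| Event | 8.5, first paragraph | Other text |
|---|---|---|
| Caused by anesthesia or undermining, observed after first device exposure | Recorded | 8.7: procedure related |
| Non-serious, starts and resolves before energy | Not required | 8.2 defines an AE by research participation; 8.5 second paragraph has AEs collected for the whole study; Table 1 has a Day 0 AE assessment |
| Serious, before energy | Not required | 8.3: report every SAE in the study period, related or not; start of that period undefined |

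The first row is sound. The second is a direct conflict. In the third, reporting to the sponsor is covered by 8.3.

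**3. A consented subject stopped before energy, traced through the sets.**

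- Protocol 5.2: has not undergone the study procedure, so not enrolled on the natural reading.
- SAP 8.1.1 (ITT): excluded, because energy must have been delivered.
- SAP 8.1.2 (PmITT): excluded, because the procedure must be completed. SAP 8.1.4 (PP) is a subset of it.
- SAP 8.1.3 (SmITT, used for additional endpoints and so for AEs): requires enrolment, so excluded under 5.2.
- SAP 8.1.8 (account of exclusions): limited to enrolled participants, so excluded under 5.2.

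The SAP defines no separate AE safety population.

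**4. Direction.** Take x subjects with a given type of AE among 65 treated. Crude proportions stand in here for the time-to-event estimates in SAP 9.4.

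- Unrecorded event in a treated subject with no other AE of that type: the true rate is (x + k)/65 and the reported rate is x/65. The shortfall is k/65, or 1.5%, 3.1% and 4.6% for k = 1, 2, 3.
- Subject stopped because of such an AE: the true rate is (x + k)/(65 + k). The shortfall is k(65 − x)/[65(65 + k)], which is never negative. With x = 0 it is 1/66 = 1.5%, 2/67 = 3.0% or 3/68 = 4.4%.
- A procedure stopped for a reason unrelated to harm would add only to the denominator, so omitting it would raise the rate slightly. The one-way statement is about omitted harms.

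**5. How often, by assumption.** With per-subject probability q, the expected number in 65 is 65q and the chance of at least one is 1 − (1 − q)^65.

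| Assumed q | Expected in 65 | Chance of at least one |
|---|---|---|
| 0.5% | 0.33 | 28% |
| 1% | 0.65 | 48% |
| 2% | 1.3 | 73% |
| 5% | 3.25 | 96% |

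For scale, zero events in 65 still leaves an exact two-sided 95% upper limit of 1 − 0.025^(1/65) = 5.5%. One omitted subject is within ordinary sampling uncertainty.

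**The case against.** The strongest reply is that the plan collects more than 8.5's opening sentence suggests. Much of it stands, and it rules out three stronger readings.

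- **That all harms from anesthesia and undermining are lost.** A reader might infer this, but 8.5 turns on when an event is observed, not when it was caused. A hematoma or nerve injury from undermining that is seen after energy is recorded, and 8.7 says how to class it.
- **That a serious pre-energy event would go unreported and escape the safety stopping review.** Section 8.3 requires SAEs to reach the sponsor within 24 hours whatever their relation to the device. Section 8.8 acts on device- or treatment-related SAEs under the 8.3 definition and on any other perceived safety concern. The undefined start of the study period needs repair, but the text does not show such an event being missed.
- **That an ineligible subject treated in error drops out of the ITT set.** This needs a strained reading of *enrolled*. SAP 8.1.4 removes important deviations only at the per-protocol stage, which implies that such subjects are in the larger sets.

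Two further points are fair. An energy-delivered set is reasonable for a post-treatment pain endpoint, which is what SAP 8.1.1 serves. And an aborted procedure would probably generate a deviation form under Protocol 10.1.

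What the reply does not cure is the analysis. A deviation form or an SAE report gives the subject no place in any denominator. SAP 3 describes enrolment by eligibility and consent alone, which could bring an aborted subject into 8.1.3 and 8.1.8, but that contradicts Protocol 5.2. The broader AE wording elsewhere likewise contradicts the one explicit start point, leaving sites to choose.

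**Conclusion.** The point holds in two specific respects. First, non-serious events that start and resolve before energy have no consistent recording rule, and the only explicit start point leaves them out. Second, a consented subject stopped before energy is, under Protocol 5.2, in no SAP analysis set and no exclusion listing.

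The omitted harms can only lower the reported procedure-related AE rates. The size is unknown and probably small: about 1.5 percentage points per omitted subject, with the chance of at least one depending entirely on an assumed rate. No primary test, success rule or power figure is affected.

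The conclusion rests on two readings: that exposure to the study product means exposure to the device, and that a procedure stopped before energy does not count as undergone. Both are natural, but neither is spelled out. This is a cheap repair worth making, not a threat to the trial's main conclusions.

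**What to change.** - **Protocol 8.5:** start AE and expected-treatment-effect recording at the first study-procedure step on Day 0, meaning the first pre-medication or anesthetic given for the study.
- **Protocol 5.2, 8.2, 8.3 and SAP 3:** align with that start. Use one definition of enrolment, and state when the study period in 8.3 begins.
- **SAP section 8:** add an AE safety set of all consented subjects in whom any study-procedure step was started, and use it for the AE rates in SAP 9.4.
- **SAP 8.1.8:** list every aborted procedure with the step reached and the reason.
- **SAP 8.1.1:** keep the energy-delivered set for the pain endpoint.

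The cost is protocol and SAP wording plus one Day 0 CRF entry, with no added visits or subjects. Procedure-related AE rates may look slightly less favourable.
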